 - a. *Community-based OUD treatment centers (Centers).* A total of 30 centers will be included as part of the proposed study (see Attachments: Letters of Support). Centers were selected because they met the following inclusion criteria: a) prescribe FDA-approved medication to treat adult patients with OUDs; b) enroll 5+ new patients per month; and c) have at least 2 staff who provide psychosocial support to OUD patients.
 - b. *Community-based OUD treatment center providers (CM Providers).* Drs. [name] and [name] will work with each participating opioid treatment center to identify front-line treatment providers and leaders eligible for the study.

Eligible providers will be any front-line treatment provider who has: a) been involved in providing psychosocial support to OUD patients on pharmacotherapy, b) an active caseload, c) been employed by the opioid treatment center at least 3 months, and d) willingness to commit to 14 months of CM training and support. All eligible treatment providers at the centers will be invited to receive the CM didactic training. However, centers will nominate 2-5 providers to serve as “CM champions”: the “CM champions” will complete periodic measures of organizational climate (described further in Measures), submit monthly audio recordings of their sessions, receive performance feedback on their audio recordings, and (for those randomized to E-ATTC) will receive performance incentives. In our experience with centers in a recent pilot study, none had more than 5 staff, so for the vast majority of sites, we expect to be able to invite all staff to participate. Thus, between 60-150 CM Providers (30 centers x 2-5 CM Providers per center) will complete measures across the three cohorts (20-50 CM Staff per cohort).

Eligible leaders will be: a) responsible for supervising frontline CM Staff, b) have been employed by the opioid treatment center at least 6 months, and c) be willing to commit to 14 months of external leadership coaching. Thus, in addition to the 60-150 CM providers, another 60 leadership staff (30 centers x 2 leaders per center) will provide data.

There is an annual staff turnover rate of approximately 30% among substance use disorder treatment providers and 20% among leadership staff. Although we invite 2-5 front-line providers from each center to participate in the study, we allow each center to send as many providers to the CM training as desired. Given the likelihood that about

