Incentive amounts are designed to enable staff to, on average, earn bonuses that during a 12-month period would comprise about 6% of their mean annual base salary of US \$45,000. Prior P4P research^{18,19} has suggested that bonuses between 4 and 7% are large enough to significantly improve staff performance, yet modest enough to be practical for community treatment centers to implement. Provision of incentives will follow the exact same schedule of provision of performance feedback reports described in 7a. Sessions must be submitted by the last day of the month and must be from that calendar month. Within 2-4 weeks following submission of recordings, providers in the E-ATTC condition will receive email notifications from research staff containing their performance feedback reports, as well as confirmation of their achievement of CM Exposure and CM Competence for the prior month. CM staff enrolled in the E-ATTC condition will receive payments via cash, check, or Clincard.

8. Data Collection Procedures.

- a. *Organizational background form.* Prior to randomization, leaders at each center will collaboratively complete an Organizational Background Form via Qualtrics. Data collected will include, but not be limited to: number of patients, proportion of patients on different OUD medications, number of staff, average staff tenure, and years in operation.
- b. *Staff surveys.* After randomization, CM staff and leadership staff will complete two online Qualtrics surveys: one at the start of the Preparation phase and one at the midpoint of the Implementation phase. The first survey (30-45 minutes) will contain the following measures: Provider Demographics, Organizational Readiness for Change, Attitudes towards CM, and putative mediators (i.e., Implementation Climate, Leadership Engagement). The second survey (15-30 minutes) will only evaluate the putative mediators. Participating staff will receive \$25 for the first and \$20 for the second survey. We attained 82% or higher completion rates on comparable staff follow-up surveys in the New England ATTC pilot.

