- i. **Implementation climate.** A 6-item measure of CM staff and leadership shared perceptions regarding the extent to which the innovation being implemented (i.e., CM) is expected, supported, and rewarded within their center.²⁵ Each item is scored on a 5-point Likert scale. This well-validated, brief measure was developed by Jacobs and colleagues, and following published guidelines, we calculate a scale mean for each staff member.
- ii. **Leadership engagement.** A 4-item measure of CM staff and leadership shared perceptions regarding the extent to which leadership is committed to, involved in, engaged in, and accountable for the implementation of the innovation (i.e., CM). Each item is scored on a 5-point Likert scale. Developed and validated as part of [name] current NIDA-funded project, this measure has demonstrated excellent internal reliability ($\alpha = .94$) and has been shown to be a significant predictor of staff-level implementation fidelity ($\beta = .18, p < .05$).²⁶

d. *Covariates.* We measure potential baseline covariates at the patient, staff, and organization level. These measures are only administered at baseline. Specific measures used include:

- i. **Baseline organization form.** A form measuring baseline characteristics including years of operation, number of patients served, and medications prescribed.
- ii. **Implementation Readiness.** A well-validated 12-item pragmatic measure developed by Shea and colleagues²⁷ will assess readiness to implement CM.
- iii. **CM Attitudes.** A brief measure of attitudes towards CM, as well as providers' perception of its effectiveness and acceptability will be administered. This measure was developed by the NIDA Clinical Trials Network and has been used in multiple NIDA funded studies.
- iv. **Provider demographics.** At the provider-level, we measure staff tenure, education level, and attitudes towards CM.

- v. Patient demographics. At the patient-level, we measure biological sex, race/ethnicity, age, and problem severity.
- vi. Patient clinical characteristics. At baseline, we administer a general measure of global health functioning. This scale was developed by the NIH funded patient-reported outcomes study and is used in multiple NIH funded studies.
- e. *Other Measures*. As noted in prior sections, we also collect some additional measures.

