 - i. *Patient contact information*. At the baseline assessment, we collect multiple forms of patient contact information, which will be stored separately from other study data. We gather this information from patients either over the phone or via face-to-face sessions and store it on paper forms kept in locked filing cabinets separate from other study measures.
 - ii. *Patient locator forms*. At the baseline assessment, patients complete locator forms and sign locator letters with contact information of 2-3 close family members or friends in order to enable us to retain participants for the follow-up assessments. These data will be stored separately from other study data. We gather this information from patients from patients either over the phone or via face-to-face sessions and store it on paper forms kept in locked filing cabinets separate from other study measures.
 - iii. *Provider CM knowledge*. Immediately following the full day training, providers will complete a measure of CM knowledge to ensure that they have sufficient understanding of CM principles to proceed to role plays. Providers that do not score at least 16 out of 20 will receive additional customized support from the ATTC trainer.

10. Analytic Plan.

- a. All analyses will be conducted following intent-to-treat principles.^{28,29} Missing data will be multiply imputed following recommendations of the National Research Council.³⁰ We will test the appropriateness of assumptions underlying the use of multiple imputation using sensitivity analyses.³¹

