- b. For the **Primary and Secondary Aims**, we test a series of multilevel models in which patients (Level 1) are embed within staff (Level 2) and within centers (Level 3). Consistent with Raudenbush and Bryk's multilevel modeling approach,³² the proportion of variance to-be-explained at each level will be examined as an initial step. Next, following a decomposed-first strategy that advocates for starting with moderation-focused hypotheses to avoid biases associated with conflated effects,³³ we conduct multilevel regressions testing the extent to which our covariates significantly moderate the hypothesized relationship between condition and outcome. We test covariates at three levels: organizational (e.g., years of operation, number of patients, medications prescribed, implementation readiness), staff (e.g., tenure, education, CM attitudes), and patient (e.g., age, race, biological sex, problem severity). If moderation is not found, covariates will be controlled for as predictors. Condition assignment (ATTC vs. E-ATTC) will be the primary independent measure of interest for analyses. In addition to reporting statistical significance, we will report the effect size (ES) using Cohen's d .³⁴
- c. For the **Exploratory Aim**, we again test a series of 3-level models. For each mediator, the average correlation within group (r_{wg}) will be computed to determine whether aggregation of staff level responses to the organizational-level is warranted. Values of r_{wg} range from -1.00 to 1.00, with values $\geq .60$ representing acceptable agreement.³⁵ Centers with r_{wg} values $< .60$ will be excluded from analysis. Exploratory analyses will apply a Baron and Kenny³⁶ style mediation approach,

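### Exploratory Aim: the mediation analysis drops randomized centers on an agreement score measured after randomization, and its listed second step leaves out the center-mean mediator that the named method requires

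*Combined protocol and SAP*

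**What the plan says.** All references are to the Combined protocol and SAP.

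- Section 10a: "All analyses will be conducted following intent-to-treat principles". No exception is made for the Exploratory Aim. The sensitivity analyses named there concern the multiple-imputation assumptions.
- Section 10c: r_wg is computed for each mediator to decide whether staff answers may be aggregated to the center. Its values are said to "range from -1.00 to 1.00", .60 or more is acceptable, and centers below that "will be excluded from analysis".
- Section 8b: "After randomization, CM staff and leadership staff will complete two online Qualtrics surveys", one at the start of Preparation and one at the midpoint of Implementation. Both carry the mediator scales. Section 10c does not say which wave supplies the mediator or r_wg.
- Section 9c: both mediators use 5-point items (six for climate, four for leadership engagement). For climate, "we calculate a scale mean for each staff member".
- Section 10c, continued: the approach is named as CWC(M), centering within context with a group mean at level 3. Three steps follow: regress the outcome on condition; regress it on condition and the group-mean-centered mediator; subtract the second condition coefficient from the first. The between-group effect is said to be the one of interest.

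**The concern.** Centers are the unit of randomization. Deleting a center on a score observed after randomization means that the arms analyzed need not be the arms randomized. The midpoint survey falls when leadership coaching and provider bonuses are running in one arm only, and the scales ask about support, reward and leadership, so agreement could plausibly differ by arm. Because r_wg is computed separately for each mediator, climate and leadership engagement could also be tested in different sets of centers. With 30 clusters, even a small loss matters for a center-level effect.

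The second issue is what a programmer would code. A mediator centered on its own center's mean carries no between-center information, so adding it cannot absorb a between-center effect of condition. A real mediated effect would then be reported as almost nothing.

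**Working it through.** The plan gives no sample-size or precision figure for the Exploratory Aim, so there is none to reproduce.

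**1. Expected number of centers excluded**

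Inputs from the documents: 30 centers; 2 to 5 CM staff per center (section 3b); two leaders per center, as "another 60 leadership staff (30 centers x 2 leaders per center) will provide data"; 5-point items. That gives 4 to 7 raters. At the completion rate cited in section 8b ("We attained 82% or higher completion rates on comparable staff follow-up surveys"), 0.82 × 4 = 3.3, so k = 3 to 7 is used.

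Assumptions, because the documents give no rater SD or null variance: uniform null on five points, variance (5² − 1)/12 = 2; normal scores; within-center rater SD of 0.5 to 0.8.

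Single-score form: r_wg = 1 − s²/2, so r_wg < .60 means s² > 0.8. Expected exclusions = 30 × P(χ² with k − 1 df > n × 0.8/SD²), with n = k or n = k − 1 according to the variance divisor. Ranges are over k = 3 to 7:

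| Rater SD | divide by k | divide by k − 1 |
|---|---|---|
| 0.5 | 0.03–0.25 | 0.12–1.22 |
| 0.6 | 0.49–1.07 | 1.14–3.25 |
| 0.7 | 2.28–2.65 | 4.01–5.86 |
| 0.8 | 4.60–5.64 | 8.31–8.69 |

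Example: k = 4, SD 0.7, divide by k − 1: 3 × 0.8/0.49 = 4.90 on 3 df, tail probability 0.179, × 30 = 5.4 centers.

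A ceiling at 5 with mean 4 lowers the SD 0.7 row to about 1.0–1.6 (divide by k) or 2.0–4.6 (divide by k − 1).

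Which form applies is not stated. One scale mean per staff member fits the single-score form. The stated range fits division by k: four raters split between 1 and 5 give s² = 4 and r_wg = −1.00, whereas division by k − 1 gives s² = 5.33 and −1.67.

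Multi-item form with J items and mean item variance v: r_wg(J) = J(1 − v/2)/[J(1 − v/2) + v/2]. This is below .60 only if v > 1.45 (J = 4) or v > 1.60 (J = 6). For leadership engagement, "this measure has demonstrated excellent internal reliability" (alpha .94), which implies an inter-item correlation of .94/(4 − 3 × .94) = .80. Simulation over both divisors then gives 0.1–1.9 exclusions at SD 0.7 and 0.7–3.7 at SD 0.8. For climate, with inter-item correlation assumed at .60–.80, the figures are 0–2.0 and 0.4–4.1.

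**2. Step two as listed**

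Let T be condition, constant within center j, and let d = m − m̄_j be the centered mediator. In balanced data d sums to zero in each center, so ΣT·d = T·Σd = 0. T and d are orthogonal, and the step-one-minus-step-two difference is zero whatever the true mediation. In unbalanced data the patient-weighted sum of d is not exactly zero, but it has no systematic relation to T.

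Simulation: three-level generalized least squares, 30 centers, variance components .25 (center), .09 (staff) and 1 (residual), condition-to-mediator 0.8, center-mean-to-outcome 0.8, so the assumed between-center mediated effect is 0.8 × 0.8 = 0.64.

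- Balanced, step two as listed: largest absolute difference about 10⁻¹⁶ in 200 runs.
- Unbalanced (2–5 staff, leaders counted in the center mean, uneven patient loads), as listed: mean 0.001, SD 0.03, largest 0.14 in 1,000 runs.
- Same unbalanced data with the center mean added: mean 0.63.

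**The case against.** **The exclusion rule.** Checking agreement before aggregating is reasonable, and the .60 rule is explicit and set in advance. Both mediators are defined as shared perceptions; where a few raters disagree, a center mean is a poor measure of that construct, and keeping such a center adds noise. This stands as a reason to check and report r_wg. It does not require removing the center from the only mediation analysis described. It is also true that intent-to-treat protects the effect of condition and not the mediator-to-outcome path, so keeping all centers does not make mediation a randomized comparison.

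**Step two.** The sentence introducing the method does call for a group mean at level 3, so an analyst who knows CWC(M) would probably include it. That stands: this is a mismatch between a correctly named method and its written steps. A reader might infer that the plan leaves the center mean out altogether; it does not.

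**Stronger readings of the exclusion.** A reader might infer that it will bias the arms. The documents do not show that agreement differs by arm, and if r_wg came from the start-of-Preparation survey the effect of condition on it would be slight. A reader might also infer that a large share of centers will be lost. The size depends on the assumed SD, index form and divisor, and it may be near zero.

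**Conclusion.** Both parts hold, for the Exploratory Aim only. The primary and secondary analyses do not use the .60 rule or the mediation steps.

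First, the .60 rule removes randomized clusters on a post-randomization measure, contrary to section 10a, with no all-centers mediation analysis beside it. Under the stated assumptions the expected loss is near zero to about 9 of 30 per mediator for SDs of 0.5 to 0.8. The SD range is itself an assumption, and a larger spread would exclude more. Differential loss by arm remains a possibility only.

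Second, step two as written cannot estimate between-center mediation. The balanced-data zero is algebraic; the unbalanced figures depend on the assumed variance components and effects.

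The unstated survey wave is a lesser point, and the verdict does not rest on it. A reader might infer that mediation of CM Sustainment is on firmer causal ground because Sustainment follows both surveys. Later timing does not remove mediator-outcome confounding, so that reading is not supported.

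**What to change.** In section 10c:

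1. Keep all randomized centers in the main mediation analysis. Report r_wg by center and arm, state its form (single-score or multi-item) and variance divisor, and run the below-.60 exclusion as a sensitivity analysis.
2. Write the center-mean mediator at level 3 into step two, alongside condition and the centered mediator, and compute the between-center mediated effect from that model.
3. Optional clarification: state which survey wave supplies the mediator and r_wg. Describe mediation of every outcome, CM Sustainment included, as associational because the mediator is not randomized. If the midpoint wave is used, note the further time-order limit for outcomes that partly precede it: CM Exposure, CM Competence, 3-month outcomes and possibly some 6-month outcomes.

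The cost is wording and one added sensitivity analysis, with no new data. The small downside is that centers without demonstrated agreement add noise to the mediator in the main analysis; the sensitivity analysis shows whether that matters.

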 - iii. **CM Sustainment**. This is a patient-level measure of the number of CM sessions delivered per patient during the 12-month Sustainment phase. Using the same protocol as for CM Exposure, data will be extracted at the end of the Sustainment phase from 25 randomly selected patients meeting eligibility criteria (i.e., newly admitted to OUD pharmacotherapy during the Sustainment phase; 25 patients * 30 sites = 750 patients). A continuous measure of the number of sessions received, as counted by the number of Medical Record Data Extraction forms completed, will be created for each patient.

b. *Patient outcomes.* Our **Secondary Aim** tests the effectiveness of the two implementation conditions (ATTC vs. E-ATTC) on two patient outcomes: Opioid Abstinence and Opioid-Related Problems.

- i. **Opioid Abstinence.** Patient abstinence from opioids will be assessed via 3- and 6-month post-baseline interviews, during which patients will self-report days of abstinence using the Timeline Followback (TLFB).²⁰ Abstinence will be corroborated via dip urine screens from Redwood Toxicology testing for: heroin/opiates, oxycontin, benzodiazepines, cocaine, methamphetamines, and THC. In addition, at the request of participating centers, single-panel screens will test for fentanyl, a highly lethal opioid not detected in multi-panel screens. A urine screen negative for all opioids (heroin/opiates, oxycontin, fentanyl) will be required for coding of 90 days abstinence. Other drug use detected via the TLFB or urine will be examined as covariates in the analysis.
- ii. **Opioid-Related Problems.** Opioid-related problems will be assessed via patient self-report at 3- and 6-months post-baseline using the Substance Problem Index,²¹ which is a count of DSM symptoms experienced by the patient (range from 0 to 11). Both Drs. [name] and [name] have successfully used this index²²⁻²⁴ in prior studies. The index will be tailored to focus specifically on problems due to opioids.

c. *Putative mediators.* Our **Exploratory Aim** tests putative mediators of implementation outcomes: implementation climate and leadership engagement. Organization-level scoring is described in **Analytic Plan**. The putative mediator scales are measured at the start of the Preparation phase and the midpoint of the Implementation phase.

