which uses centering within context and includes a group mean at level-3 (CWC[M]).³⁷ Procedurally, first the outcome will be regressed on the condition variable (ATTC vs. E-ATTC) in a multi-level regression. Next, the outcome will be predicted by both condition and the group mean centered mediator (e.g., implementation climate) in a multi-level regression. Third, the mediational effect will be calculated by subtracting the estimated coefficient associated with condition in step two from the estimated coefficient associated with condition in step one. This method will allow the between-group mediation effect to be partitioned from the within-group mediation effect, which is important since between-group mediation is the effect of interest. Although significance of the mediation effect will be calculated using the Freedman and Schatzkin³⁸ *t* statistic, we also will report ES, which are not influenced by power.

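### The mediation procedure names no survey wave for the mediator and does not adjust for the start-of-Preparation climate or leadership score, so pre-existing center differences can be counted as mediation

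*Combined protocol and SAP*

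**What the plan says.** Section 9.c sets two measurement times: "The putative mediator scales are measured at the start of the Preparation phase and the midpoint of the Implementation phase". Section 8.b places the first of these after assignment: "After randomization, CM staff and leadership staff will complete two online Qualtrics surveys: one at the start of the Preparation phase". On the later one it says: "The second survey (15-30 minutes) will only evaluate the putative mediators".

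Section 10.c then gives the mediation procedure term by term:

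- Step one: "first the outcome will be regressed on the condition variable (ATTC vs. E-ATTC) in a multi-level regression".
- Step two: "Next, the outcome will be predicted by both condition and the group mean centered mediator (e.g., implementation climate) in a multi-level regression". The centering method named there also carries the center mean at level 3.
- Estimate: "the mediational effect will be calculated by subtracting the estimated coefficient associated with condition in step two" from the condition coefficient in step one.
- Target: "between-group mediation is the effect of interest".
- Test: "significance of the mediation effect will be calculated using the Freedman and Schatzkin" t statistic.

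No step states which wave supplies the mediator, and neither contains the first-wave score or a change score. The covariates in 9.d are described as baseline-only measures and do not include the two mediator scales. The covariates in 10.b belong to the Primary and Secondary Aims and do not name those scales either. Urn randomization (section B.2, study design) balances patient volume and percent on methadone, not climate or leadership.

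**The concern.** Condition is randomized; the mediator is not. A center that begins with a supportive climate or engaged leaders may still score well at mid-Implementation, and may also deliver more CM for reasons that predate the midpoint score. When the starting score is left out, the midpoint score stands in for it in step two. The mediator coefficient then picks up the prior link, the condition coefficient shrinks, and the shrinkage is reported as mediation. Because this is a bias in the between-center comparison, recruiting more centers would not remove it.

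At stake is the Exploratory Aim's answer on why the enhanced strategy works, which the study purpose lists among the trial's goals. The unstated wave adds a second gap: the analyst could choose it after seeing the data.

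**Working it through.** The documents give no alpha, power or effect size for the mediation aim, so there is no planned figure to reproduce.

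**Inputs from the documents.** 30 centers; two survey waves; difference-in-coefficients estimate; Freedman-Schatzkin t; between-center effect.

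**Assumed inputs** (none is in the documents), in center-level SD units: 15 centers per arm; two-sided 5% test; condition effect on the midpoint mediator a = 0.8; start-to-midpoint correlation ρ from 0.3 to 0.7; effect of the starting score on the outcome d from 0.3 to 0.5; direct condition effect 0.5.

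**Model with no true mediator effect.** Let T be condition, M0 the starting score, M1 the midpoint score and Y the outcome:

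- M1 = ρ·M0 + a·T + error
- Y = 0.5·T + d·M0 + error

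Step one returns 0.5 for T on average. In step two, given T, M1 has variance 1 and covariance ρ·d with Y. Its coefficient is therefore ρ·d, and the T coefficient is 0.5 − a·ρ·d. The difference, all of it false, is **a·ρ·d**:

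- 0.8 × 0.3 × 0.3 = 0.072
- 0.8 × 0.6 × 0.4 = 0.192
- 0.8 × 0.7 × 0.5 = 0.280

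**Simulation** (ordinary least squares on 30 center means, planned t, several thousand runs per row):

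| ρ / d | False effect, as planned | False positives, as planned | With M0 in both steps |
|---|---|---|---|
| 0.3 / 0.3 | 0.07 to 0.08 SD | about 6% | about 0 SD, 4% |
| 0.6 / 0.4 | 0.19 SD | 21% to 22% | about 0 SD, 5% |
| 0.7 / 0.5 | 0.28 SD | 43% | about 0 SD, 5% |

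The last column assumes that M0 is measured without error and is the only confounder.

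**If condition does not move the mediator (a = 0).** The average bias is zero. Chance imbalance remains: the arm difference in starting score has standard error √(2/15) = 0.37 SD and exceeds 0.5 SD in 17% of randomizations. Planned-test false positives are then about 3% at 0.3/0.3 and 21% at 0.7/0.5.

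**If M0 is measured with reliability 0.7** (ρ = 0.6, d = 0.4). The residual false effect is a × ρ·d·(1 − 0.7) / (1 − 0.7·ρ²) = 0.8 × 0.072 / 0.748 = 0.077 SD, with about 7% false positives. The correction is large but partial.

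**If condition has already shifted the first survey by s** (true mediator effect 0.4, d = 0, ρ = 0.6, total a still 0.8). The true mediated effect is 0.8 × 0.4 = 0.32 SD. The adjusted estimate is 0.4 × (0.8 − 0.6·s):

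- s = 0.3: 0.4 × 0.62 = 0.248
- s = 0.5: 0.4 × 0.50 = 0.200

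The unadjusted estimate stays near 0.32.

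**Power cost** when the first score does not predict the outcome (true mediator effect 0.4). Under the planned t, power falls from about 50% to about 34% at ρ = 0.6, and to roughly 27% to 29% at ρ = 0.7.

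**The case against.** **The first score is not a pre-randomization baseline.** This stands. Section 8.b puts the survey after randomization. The climate scale asks how far CM is expected, supported and rewarded, while one arm is to receive bonuses and leadership coaching. The documents do not say that staff answer before learning their assignment. If they know it, adjustment can remove true mediation, as the last estimates in the working show. A reader might infer that adding the score simply restores an unbiased answer; the documents do not support that.

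**The size is assumed.** This also stands. The surveys are about 9.5 months apart (5 months plus half of 9). Section B.3 expects 2 to 5 providers and 2 leaders per center, with annual turnover of about 30% and 20% and replacement of departing CM staff. All of this could weaken ρ. At 0.3/0.3 the inflation is slight. A reader might infer that the planned analysis is biased whatever the data; that goes too far. The bias needs the starting score to predict both later quantities and condition to move the mediator.

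**Silence is not exclusion.** This stands in part. Section 10.c again uses three-level models, so the covariates of 10.b, which are listed only as examples, might carry over. But 10.c does not say so, and baseline implementation readiness and CM attitudes would be only partial proxies.

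**The centering method handles it.** This fails. Centering separates within-center from between-center variation. Pre-existing differences between centers stay in the between-center part, which is the declared target.

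**Adjustment costs power.** True, and the cost under the planned t is not trivial. But the unadjusted test does not hold its error rate when the starting score matters.

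**Conclusion.** The concern holds in conditional form. Section 10.c leaves the mediator wave unstated and lists no adjustment for a score the trial already collects. If starting climate or leadership predicts both the midpoint score and the outcome, and condition moves the mediator, the planned estimate overstates mediation. The overstatement ranges from slight to serious over the assumed correlations; the omission is plain from the text, but its size cannot be known from the documents. The calculation works on center means rather than the full three-level model, and dropping centers with agreement below .60, as 10.c provides, would leave fewer than 30.

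A reader might also infer that the trial's main conclusions are at risk. They are not: the Primary and Secondary Aims do not use the mediation models. This is a cheap improvement to an exploratory analysis.

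**What to change.** In 10.c:

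1. Name the mid-Implementation center mean of each scale as the mediator.
2. Put the first-survey center mean of the same scale into both outcome steps, so that the two condition coefficients stay comparable, and into the condition-to-mediator model.
3. Describe that score as a start-of-Preparation, post-randomization measure, and where feasible obtain it before staff learn their assignment.
4. Report the unadjusted model beside the adjusted one, stating that the first is open to pre-existing center differences and the second to any early effect of assignment on the first survey.

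The cost is SAP wording and one center-level degree of freedom, plus the possible power loss shown in the working. No new data are needed. Earlier timing of the first survey, where feasible, would be a change of procedure.
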